3.1 RNActive® technology

During translation mRNA serves as the template for protein synthesis and mRNA-based vaccines offer the possibility to vaccinate against any infectious disease that is preventable by providing or increasing the immune response against the protein antigen. However, mRNA molecules are highly unstable under physiological conditions, limiting their therapeutic application [11]. Research into achieving ribonucleic acid (RNA) stability has led to the development of different RNA delivery systems [12], including CureVac's mRNA technology (RNActive®).

The RNActive® technology employs formulated mRNA as a vaccine vector to allow for direct translation of target protein antigens within a recipient's cells. RNActive® vaccines formulated with lipid nanoparticles (LNPs) consist of an mRNA encoding the antigen of interest, which is encapsulated by LNPs. The mRNA provides strong antigen expression. The encapsulation of mRNA in LNPs is intended to facilitate and enhance the uptake of mRNA by cells. As a result of mRNA translation, antigen presentation and immune stimulation, strong and persistent adaptive immune responses against the encoded antigens are induced in animal models [13, 14].

A phase I trial evaluating the first candidate rabies mRNA vaccine formulated with protamine (CV-7201-102) induced boostable virus-neutralizing antibodies after needle-free (intradermal [i.d.] or intramuscular [i.m.]) injection, whereas needle-based (i.d. and i.m.) injection was ineffective [15]. The vaccine appeared generally safe with an acceptable reactogenicity profile. This trial provided important guidance for advances in CureVac's mRNA technology (RNActive®) particularly with respect to development of improved vaccine candidates formulated with lipid nanoparticles (LNP), which have been demonstrated to efficiently deliver mRNA in vivo to the cytoplasm of cells, where the encoded antigens are translated into proteins able to elicit antigen-specific immune responses [16].

The new candidate rabies mRNA vaccine, CV7202, is composed of R1803 (the identical active pharmaceutical ingredient [API], used in CV-7201-102), encapsulated in the novel LNP delivery system. mRNA-based vaccines based on this new delivery system have been shown to induce substantially higher and more durable virus-neutralizing antibody titers (VNTs) compared with protamine-formulated vaccines in several animal models [13] and elicit comparable responses in NHPs to those seen with licensed vaccines [17].

The current clinical study CV-7202-104 is ongoing with 10 subjects having received CV7202 up to date and being followed-up. Therefore, only preliminary clinical safety and immunogenicity data are available at this time.

The proposed trial will assess the safety, reactogenicity and immunogenicity of different doses of CV7202 in healthy adult subjects (18–40 years of age) administered i.m. as one or two doses. The active control, Rabipur® will be administered in previously unvaccinated subjects, as the three recommended doses.

The trial will be conducted in accordance with the protocol, the ICH-GCP Guidelines [1], European Medicines Agency (EMA) guidelines for first-in-human (FIH) clinical trials [22] and applicable regulatory requirements.

Refer to the current Investigator's Brochure (IB) for CV7202 for additional product information [17].

4 Objectives and Endpoints

The primary, secondary, and exploratory objectives and endpoints of this trial are listed in sections 4.1 and 4.2.

4.1 Objectives

Primary Objective:

To assess the safety and reactogenicity profile of CV7202 administered i.m. to healthy adults (18–40 years old), as a range of doses (1, 2 and 5 µg) in one- or two-dose regimens.

Secondary Objectives:

For safety

- To assess the safety profile of CV7202 administered i.m. to healthy adults (18–40 years old), as a range of doses (1, 2 and 5 µg) in one- or two-dose regimens in the period from 12 to 24 months post last dose.

For the characterization of the humoral immune response

- To evaluate the potential protective immune responses to CV7202 and Rabipur® in healthy adults (18–40 years old), by assessing the percentages of subjects with rabies-specific serum VNTs ≥ 0.5 IU/ml.
- To evaluate the immunogenicity (VNTs) of CV7202 administered to healthy adults (18–40 years old), as a range of doses (1, 2 and 5 µg) in one- or two-dose regimens and the immunogenicity of Rabipur® administered in a 3-dose regimen.

Exploratory Objectives:

For the evaluation of the innate immune response

- To evaluate the innate immune response to one or two doses of CV7202 compared with baseline.

For the evaluation of antigen specific T-cell response

- To evaluate the frequencies and functionalities of rabies virus glycoprotein (RABV-G)-specific T cells after one or two doses of CV7202 compared with baseline.

For the evaluation and characterization of the B-cell response

- To evaluate the frequencies of RABV-G-specific B cells after one or two doses of CV7202 compared with baseline.
- To evaluate the effect of vaccination on B-cell phenotype and activation after one or two doses of CV7202 compared with baseline.
- To evaluate the effect of vaccination on B-cell clonality after one or two doses of CV7202 compared with baseline.

For the characterization of the humoral immune response

- To evaluate RABV-G-specific antibody responses throughout the trial including the follow-up period by assessing IgM, IgG and IgA levels.

- To characterize the nature and quality of the RABV-G-specific antibody response, by measuring the serum affinity and avidity after one or two doses of CV7202 and the breadth of neutralization against heterologous lyssaviruses with variant epitopes.

4.2 Endpoints

Primary Endpoints:

- The percentages of subjects with, and the frequencies and intensities of solicited local adverse events (AEs) reported on the day of vaccination and the 7 subsequent days (Days 1-8).
- The percentages of subjects with, and the frequencies, intensities and relationship to vaccination, of solicited systemic AEs reported on the day of vaccination and the 7 subsequent days (Days 1-8).
- The duration (in days) of solicited local AE, of solicited systemic AE and of the individual solicited AEs.
- The percentages of subjects with and frequencies and intensities of any unsolicited and related unsolicited AEs reported on the day of vaccination and the 28 subsequent days (Days 1-29).
- The percentages of subjects with and frequencies and relationship to vaccination, of any serious adverse events (SAEs) and any MAAEs up to 12 months post last dose.
- The percentages of subjects with and frequencies and relationship to vaccination of any adverse events of special interest (AESIs) up to 12 months post vaccination.

Secondary Endpoints:

For safety

- The percentages of subjects with and frequencies of SAEs and MAAEs related to study vaccination from 12 months post last dose up to 24 months post last dose (trial end).
- The percentages of subjects with and frequencies and relationship to vaccination of any AESIs from 12 months post last dose up to 24 months post last dose (trial end).

For the characterization of the humoral immune response

- Percentages of subjects with rabies-specific serum VNTs ≥ 0.5 IU/ml by trial group on Days 1 (pre-vaccination), 15, 43, and 12, 18* and 24* months post last dose.
- Serum geometric mean titers (GMTs) of VNTs by trial group on Days 1, 8, 15, 29, 36, 43, 57, 91, and 6 and 12, 18* and 24* months post-last dose.

* Will be performed only in subjects with detectable RABV-G-specific IgG at 6 months after the last vaccination or Day 91 if the Month 6 blood sample is not available.

Exploratory Endpoints:

For the evaluation of the innate immune response:

- Serum cytokine concentrations* including but not limited to CXCL10, CCL3, IL-6, TNF- α and IFN- γ , at pre-vaccination and 4 hours post-vaccination on Day 1, and Days 2 or 3** and 8 after each vaccination.
- Transcriptome profiling* on the day of vaccination at pre-vaccination, and Days 2 or 3** and 8 after each vaccination.

* Will be performed in the first 5 subjects in Group 2 (** on Day 3) and all subjects in Groups 3 and 4 (** on Day 2). Note that Day 3 was planned in the original protocol and only applies to subjects in Groups 1 and 2 who were already enrolled and vaccinated before this protocol amendment was issued. Day 2 applies to all other subjects.

For the evaluation of antigen specific T-cell response:

- The frequencies and functionalities of RABV-G-specific T cells in peripheral blood from the first 5 subjects in Group 2 and all subjects in Groups 3 and 4 on Days 1, 8, 36, 91*, and 6* and 12* months post-last dose.

* For groups that have shown a significant T-cell response at Day 8 or 36 compared to baseline.

For the evaluation and characterization of the B cell response

- The frequencies of RABV-G-specific B cells in peripheral blood from the first 5 subjects in Group 2 and all subjects in Groups 3 and 4 on Days 1, 8, 36, 91*, and 6* and 12* months post-last dose.
- The frequencies and activation status of phenotypically distinct subsets of B cell populations, including but not limited to naïve and memory B cells, plasmablasts and plasma cells for the first 5 subjects in Group 2 and all subjects in Groups 3 and 4 on Days 1, 8, 36, 91*, and 6* and 12* months post-last dose.
- Sequencing of B-cell receptors (BCR) of circulating B cells on Days 1, 8, 29, 36, 57, 91*, and 6* and 12* months post-last dose.

* For groups that have shown a significant B-cell response at Day 8 or 36 compared to baseline.

For the characterization of the humoral immune response:

- RABV-G-specific IgM, IgG and IgA levels measured by ELISA on Days 1, 8, 15, 29, 36, 43, 57, 91, and 6 and 12 months post-last dose.
- RABV-G-specific IgG levels measured by ELISA 18* and 24* months post-last dose.
- Identification of epitopes recognized by vaccine-induced antibodies on Days 1, 15, 43, and 2, 6 and 12 months post-last dose**.
- Measurement of RABV-G-specific antibody avidity and affinity on Days 1, 15, 43, and 2, 6 and 12 months post-last dose**.

- Measurement of VNTs against additional heterologous lyssaviruses on Days 1, 15, 43, and 2, 6 and 12 months post-last dose**.

* Will be performed only in subjects with detectable RABV-G-specific IgG at 6 months after the last vaccination or Day 91 if the Month 6 blood sample is not available.

[figure not shown]
** Will be performed only on selected samples with VNT >0.5 IU/ml.

5 Trial Design

5.1 Overall Design

This is a non-randomized, open label, controlled, dose-escalation, phase I clinical trial to evaluate the safety, reactogenicity and immunogenicity of one or two i.m. administrations of candidate rabies mRNA vaccine CV7202 in healthy adult subjects. Approximately 52 subjects will be enrolled sequentially in up to 4 trial groups to receive either a dose of CV7202 containing different mRNA content or Rabipur®. In a first CV7202 group, 10 subjects have received a dose containing 5 µg mRNA. A dose of 1 or 2 µg mRNA will be administered to 2 additional groups of 16 subjects each, of whom 8 in each group will be administered a second dose 28 days later. A control group of 10 subjects will receive 3 doses of the licensed vaccine Rabipur® according to the manufacturer's recommendations. Safety and immunogenicity assessments will be made up to 2 years following the last dose administration. Specified safety data will be reviewed by an internal safety review committee (iSRC) and a data safety monitoring board (DSMB) on a pre-defined schedule.

Figure 5.1 CV-7202-104 Trial Design

5.1.1 Dose-finding Schedule, Enrolment Plan

Enrolment will be staggered in Groups 2 to 4 to ensure the safety of the participating subjects (Table 2.2). Enrolment into Group 1 (1.0 ml Rabipur®) will not be staggered, since the clinical safety of Rabipur® is well-established.

CV7202 Groups: In Group 2, the first 5 subjects sequentially received the first dose with a 2 working-day interval between subject #1 (e.g. Week 1 – Day 1 – Monday) and subjects #2 and #3 (e.g. Week 1- Day 3 – Wednesday) and were observed for 2 days. Subjects #4 and #5 received their first dose one week after subject #1 (e.g. Week 2 – Day 1 – Monday). Once the fifth subject in the group had been vaccinated and followed up for at least 2 working days, safety data for the first 5 subjects were

reviewed by the iSRC. Following iSRC approval, the remaining 5 subjects in the group were enrolled and received the first dose.

In Groups 3 and 4, the first 4 subjects will also be enrolled using a staggered approach. The first 4 subjects will sequentially receive the first dose with a 2 working-day interval between subject #1 (e.g. Week 1 – Day 1 – Monday) and subject #2 (e.g. Week 1- Day 3 – Wednesday) and will be observed for 2 days. A phone call will be performed after 2 days to collect safety information. Subjects #3 and #4 will receive their first dose at the earliest one week after subject #1 (e.g. Week 2 – Day 1 – Monday). All data obtained from these sentinel subjects (at least until 2 days after the vaccinations) must be entered continuously into the eCRF, at the latest within 24 hours, to allow a timely safety assessment. Once the fourth subject in the group has been vaccinated and followed up for at least 2 working days, safety data recorded in the eCRF for the first 4 subjects will be reviewed by the iSRC. Following iSRC approval, the remaining 12 subjects in the group will be enrolled and receive the first dose. In addition, the staggered enrolment may be extended to the subsequent subjects to be enrolled in Groups 3 and 4. The number of subjects in this extended staggered enrolment may be further established by the investigator, sponsor or DSMB based on the data obtained in earlier enrolled subjects in these groups. The DSMB will review safety data for an observation period of 28 days following administration of the first dose for all subjects in each dose group prior to enrolment into the next dose group (i.e. from the 1 µg dose level Group 3 to the 2 µg dose level Group 4). Before administration of the second dose of CV7202, the iSRC will review all available accumulated safety data from all subjects having already received a second dose.

Enrolment in each dose group can proceed as follows for a duration of a minimum of 7 weeks per group. A slower enrolment schedule can be followed in agreement with the investigator and sponsor, if needed with input from the iSRC or DSMB:

- **Week 1:** Start enrolment in Group 3 (up to 2 subjects). Subject #1 on Day 1, subject #2 on Day 3.
- **Week 2:** Enrol subjects #3 and 4 on Day 1 and prepare iSRC review of AEs and available safety data following 2 days' observation.
- **From Week 3:** Enrol the remainder of the subjects (i.e. 12 subjects for Groups 3 and 4). Extended staggered enrolment (e.g. for subjects #5 to 10 or beyond) can be implemented as needed.
- **From Week 7:** Collect solicited AEs, unsolicited AEs, SAEs and safety laboratory data, and prepare DSMB review.
- Favorable DSMB decision: Start the enrolment cycle for the next dose level group.

The staggered approach to dose administration does not apply to Dose 2.

5.1.2 Stopping Rules

For dose escalation (group)

At each planned safety review, safety data will be reviewed and a GO/NO GO decision made accordingly for enrolment of further subjects and administration of subsequent doses.

Enrolment or administration at the given dose level will be temporarily halted and only continued after DSMB approval and approval by the competent authority following the occurrence of:

- Any related SAE in the opinion of the principal investigator (PI), the DSMB and/or the iSRC.
- Related severe AEs of the same kind in $\geq 20\%$ of the subjects in one group with the following exceptions:
 - Transient grade 3 chills, fatigue, headache, fever, myalgia or arthralgia resolving within 24 hours to grade ≤ 2 .
 - Transient grade 3 local AEs reducing to grade ≤ 2 within 48 hours.

Based on the review of the data, the DSMB will decide about temporary or permanent stopping of dosing in the given and eventually also lower dose groups (pertaining to the 2nd dose administration). After a temporary halt further measures for safety monitoring (i.e. additional safety visits including safety blood sampling at additional time points) may also be introduced based on DSMB recommendation.

For further CV7202 dose administration (subject)

Subjects must not receive a second dose of CV7202 in the event of:

- Occurrence of an allergic/anaphylactic reaction after the first dose.
- Any related SAE in the opinion of the PI, the DSMB and/or the iSRC.
- Any related severe (grade 3) AEs with the following exceptions:
 - Transient grade 3 chills, fatigue, headache, fever, myalgia or arthralgia resolving within 24 hours to grade ≤ 2 .
 - Transient grade 3 local reactions resolving to grade ≤ 2 within 48 hours.

If these reactions occur, the subject must not receive additional vaccinations but is encouraged to continue in trial participation for safety reasons, including collection of safety blood samples. Immunogenicity assessments may be performed at the investigator's discretion and if the subject agrees.

5.1.3 Timing of Blood Collection for Safety and Immunogenicity Parameters

Blood samples will be drawn as follows:

- Safety assessments: Pre-screening, screening, Days 1, 2 or 3**, 8, 15, 29, 30 or 31**, 36, 57, Day 91, Month 6* (Day 181 [1-dose groups] and Day 209 [2-dose groups and Group 1 (Rabipur[®])]) and Month 12* (Day 365 [1-dose groups] and Day 393 [2-dose groups and Group 1 (Rabipur[®])]).

** In case a site visit is not possible due to the public health emergency related to COVID-19, the blood sample for safety assessment at Month 6 and Month 12 should be collected at Visit 14A and Visit 15A, respectively, only in case restrictive measures related to COVID-19 no longer prevent site visits (refer to Section 9.4.16 and 9.4.17 for details). If no blood sampling could be performed at Visit 15 and 15A (Month 12), the end-of-trial blood sample for safety assessment may be performed at Visit 17 (Month 24).*

- Immunogenicity assessments: Days 1, 2 or 3**, 8, 15, 29, 30 or 31**, 36, 43, 57, Day 91, Month 6* (Day 181 [1-dose groups] and Day 209 [2-dose groups and Group 1 (Rabipur®)]), Month 12* (Day 365 [1-dose groups] and Day 393 [2-dose groups and Group 1 (Rabipur®)]), Month 18* (Day 547) and Month 24* (Day 729).

** In case a site visit is not possible due to the public health emergency related to COVID-19, the blood sample for immunogenicity assessments should be collected at Visits A, only in case restrictive measures related to COVID-19 no longer prevent site visits (refer to Sections 9.4.16 to 9.4.19 for details).*

** Days 3 and 31 were planned in the original protocol and only apply to subjects in Groups 1 and 2 who were already enrolled and vaccinated before this protocol amendment was issued. Days 2 and 30 apply to all other subjects.

Refer to the schedule of activities in Table 2.1 and Section 9.5.

5.2 Subject and Trial Completion

Subjects will be enrolled at pre-screening (Day -90 to -1) to receive either CV7202 starting Day 1 as 1 dose or 2 doses (at least 28 days apart), or 3 doses of control vaccine (Rabipur®). Follow-up for safety and immunogenicity is planned up to 24 months after the last dose, therefore the expected duration of participation for each subject is approximately 24 months after the last dose.

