| | 
Primary and secondary safety and reactogenicity will be assessed as follows:
 
1. AEs (type, intensity, frequency and relationship to vaccination), i.e. incidence and severity of AEs for both solicited local and systemic events (reported on the day of vaccination and the 7 subsequent days [Days 1-8]) and unsolicited events (reported on the day of vaccination and the 28 subsequent days [Days 1-29]).2. SAEs, MAAEs and AEs leading to trial or vaccine withdrawal up to 12 months post last dose. After Visit 15 (Month 12), only SAEs and MAAEs that according to the investigator are considered to be related to study vaccination will be collected.3. Intercurrent medical conditions and AESIs throughout the trial.4. Local reactogenicity assessment of injection site in all subjects. 
Further safety assessments will be conducted based on vital signs and laboratory assessments. Results will be summarized in tables and supported by subject level listings.
 
Secondary immunogenicity endpoints:
 
1. Number and percentage of subjects having VNTs ≥ 0.5 IU/ml on Days 1, 15, 43, and 12, 18 and 24 months post last dose.2. Individual functional antibody titers, GMTs and range of titers in sera collected on Days 1, 8, 15, 29, 36, 43, 57, and 12, 18 and 24 months post last dose. 
Further immunogenicity assessments will be based on VNTs, RABV-G-specific immunoglobulins (Ig) IgG, IgM and IgA serum antibodies and other immunogenicity-related parameters throughout the duration of the trial. Results will be summarized in tables, figures and supported by subject level listings.
 
No statistically-based sample size estimation was performed.
 |
|--|--|

2 Schedule of Activities

Table 2.1 Schedule of Activities

| Visit Type | Procedure | References | Pre-screening | Screening | Clinic visit | | Phone call | Clinic visit | | | | Phone call | Clinic visit | | | | Clinic visit*** | | | | | | | | |
|--|--|------------|---------------|------------|--------------|---------|------------|--------------|-------|-------|-------|------------|--------------|-------|-------|-------|-----------------|--------|---------|--------|---------|--------|---------|--------|----------|
| | | | -90 to -1* | -30 to -1* | 1 | 2† | 3 | 8 | 10 | 15 | 29 | 30#† | 31 | 36 | 43 | 57 | 91 | M6 | | M12 | | M18 | | M24 | |

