| | | | N/A | N/A | N/A | +/- 2** | - | +1 | -1/+2 | -1/+2 | +/- 2 | +/- 2** | - | -1/+2 | +/- 2 | +/- 2 | +/- 7 | +/- 14 | + 15-90 | +/- 30 | + 31-90 | +/- 30 | + 31-90 | +/- 30 | + 31-180 |
| Visit Number | Visit Window (days) | Visit Type | 1 | 2 | 3 | 4 | - | 5 | 6 | 7 | 8 | 9 | - | 10 | 11 | 12 | 13 | 14 | 14A | 15 | 15A | 16 | 16A | 17 | 17A |
| Signed Informed Consent ^a | 9.4.1 | | | | | | | | | | | | | | | | | | | | | | | | |
| Medical History | 9.4.1 | | | | | | | | | | | | | | | | | | | | | | | | |
| Inclusion/Exclusion criteria | 6.1, 6.2, 9.4.1, 9.4.2, 9.4.3 | | | | | | | | | | | | | | | | | | | | | | | | |
| Vaccine delay recommendations | 6.3, 9.4.3, 9.4.6, 9.4.9 | | | | | | | | | | | | | | | | | | | | | | | | |
| Demographics | 9.4.1 | | | | | | | | | | | | | | | | | | | | | | | | |
| Pregnancy Test | 9.4.2, 9.4.3, 9.4.6, 9.4.9 | | | | | | | | | | | | | | | | | | | | | | | | |
| Vaccination | | | | | | | | | | | | | | | | | | | | | | | | | |
| CV7202 | 9.4.3, 9.4.9 | | | | | | | | | | | | | | | | | | | | | | | | |
| Rabipur® | 9.4.3, 9.4.6, 9.4.9 | | | | | | | | | | | | | | | | | | | | | | | | |
| Safety monitoring | | | | | | | | | | | | | | | | | | | | | | | | | |
| Physical Examination ^e | 9.4.2-9.4.11, 9.4.14, 9.4.15, 9.4.17, 0 | | | | | | | | | | | | | | | | | | | | | | | | |
| 12-lead Electrocardiogram | 9.4.2 | | | | | | | | | | | | | | | | | | | | | | | | |
| Vital signs ^f | 9.4.1, 9.4.3-9.4.11, 9.4.17, 0 | | | | | | | | | | | | | | | | | | | | | | | | |
| Post-injection vaccination site reactogenicity assessment ^g | 9.4.3-9.4.7, 9.4.9-9.4.10 | | | | | | | | | | | | | | | | | | | | | | | | |
| Diary dispensed/training ^h | 9.4.3, 9.4.5, 9.4.9 | | | | | | | | | | | | | | | | | | | | | | | | |
| Diary review/reminder ^h | 9.4.4-9.4.14 | | | | | | | | | | | | | | | | | | | | | | | | |
| Diary collection ^h | 9.4.5, 9.4.9, 9.4.14 | | | | | | | | | | | | | | | | | | | | | | | | |
| Assess all post-dose solicited AEs | 9.4.3-9.4.12 | | | | | | | | | | | | | | | | | | | | | | | | |
| Assess all post-dose unsolicited AEs | 9.4.3-9.4.14 | | | | | | | | | | | | | | | | | | | | | | | | |
| Assess all SAEs | 9.4.3-9.4.17 | | | | | | | | | | | | | | | | | | | | | | | | |
| Assess all MAAEs | 9.4.3-9.4.17 | | | | | | | | | | | | | | | | | | | | | | | | |
| Assess AEs leading to premature withdrawal | 9.4.3-9.4.17 | | | | | | | | | | | | | | | | | | | | | | | | |

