5.7 Justification for Dose

The clinical dose range of 5-200 µg was justified based on data from two repeat dose toxicity studies (in rat and rabbit) and local reactogenicity and immunogenicity data from a pharmacology study in cynomolgus monkeys.

The no observed adverse effect level (NOAEL) of CV7202 was calculated for both rat and rabbit. Rabbit was the most sensitive species. Doses intended for the phase 1 study were evaluated using two different approaches based on the NOAEL in rabbit. Normalization of dose based on a direct mg/kg conversion of the NOAEL provided a human equivalent dose of 800 µg which is approximately 4-fold greater than the highest anticipated clinical dose of 200 µg. Allometric scaling provided a conservative maximum recommended starting dose of 26 µg which is approximately 5-fold the starting dose of 5 µg. Furthermore, toxicology studies evaluated animals which were administered 4 injections at weekly intervals while human subjects will receive a single injection or two injections at least 28 days apart. Doses up to 210 µg in cynomolgus monkeys were associated with only minimal to mild reactogenicity at the injection sites.

Pharmacology data from a study of cynomolgus monkeys support the clinical dose range. After a single i.m. injection in cynomolgus monkeys of 1 µg CV7202, VNTs above the threshold of protection were observed as early as Day 28 and were still detected six months later. By extrapolation, a dose of 1 µg in a monkey (0.3 µg/kg) would represent an equivalent dose of 5-15 µg in a human. Thus, it is possible that CV7202 will elicit an immune response in human subjects from the initially defined clinical starting dose of 5 µg.

Based on the reactogenicity and immunogenicity results from the first 10 subjects vaccinated with CV7202 at the 5 µg dose level in the current trial, the dose ranges to be tested in the other groups have been lowered to 1 and 2 µg.

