4. TRIAL DESIGN AND PLAN

This is a non-randomized, open label, controlled, dose-escalation, phase I clinical trial to evaluate the safety, reactogenicity, and immunogenicity of 1 or 2 i.m. administrations of candidate rabies messenger ribonucleic acid (mRNA) vaccine CV7202 in healthy adult subjects.

Subjects will be enrolled in 2 trial sites, 1 in Germany, 1 in Belgium.

Approximately 52 subjects will be enrolled sequentially in up to 4 trial groups to receive either a dose of CV7202 containing different mRNA content or Rabipur. In a first CV7202 group, 10 subjects have received a dose containing 5 µg mRNA. A dose of 1 or 2 µg mRNA will be administered to 2 additional groups of 16 subjects each, of whom 8 in each group will be administered a second dose 28 days later. A control group of 10 subjects will receive 3 doses of the licensed vaccine Rabipur according to the manufacturer's recommendations. Safety and immunogenicity assessments will be made up to 2 years following the last dose administration.

Specified safety data will be reviewed by an internal safety review committee and a data safety monitoring board on a pre-defined schedule. At each planned safety review, safety data will be reviewed, and a GO/NO GO decision made accordingly for enrollment of further subjects and administration of subsequent doses.

Enrollment will be staggered in Groups 2 to 4 to ensure the safety of the participating subjects. Enrollment into Group 1 (1.0 ml Rabipur) will not be staggered, since the clinical safety of Rabipur is well established.

Subjects will be enrolled at pre-screening (Day -90 to -1) to receive either CV7202 starting on Day 1 as 1 dose or 2 doses (at least 28 days apart), or 3 doses of control vaccine (Rabipur). Follow-up for safety and immunogenicity is planned up to 24 months after the last dose; therefore, the expected duration of participation for each subject is approximately 24 months after the last dose.

Please refer to protocol section 5 for more details of trial design, protocol section 6 for trial population and protocol section 7 for discontinuation/withdrawal criteria.

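### The Visit 8 window allows CV7202 Dose 2 at 26 or 27 days against a stated minimum of 28, and the SAP's fixed-day AE split fits only Day 29 dosing

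*Protocol*

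**What the plan says.** **The minimum interval.** Three places give 28 days as a floor for the CV7202 dose pair:
- Protocol 5.2: "to receive either CV7202 starting Day 1 as 1 dose or 2 doses (at least 28 days apart").
- Protocol 5.7, where animals dosed weekly are contrasted with the trial: "while human subjects will receive a single injection or two injections at least 28 days apart".
- SAP section 4: "as 1 dose or 2 doses (at least 28 days apart").

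Protocol 5.1 gives the nominal plan: "of whom 8 in each group will be administered a second dose 28 days later".

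**The visit window.** The Table 2.1 notes and protocol 9.4.9 place Dose 2 for Groups 3a and 4a at Visit 8, Day 29. The day header of Table 2.1 begins "90 to -1* | -30 to -1* | 1 | 2† | 3 | 8 | 10 | 15 | 29 | 30" and its window row begins "N/A | N/A | N/A | +/- 2 | - | +1 | -1/+2 | -1/+2 | +/- 2 | +/- 2". In the document the fourth and tenth window entries also carry a double asterisk. That footnote turns the two units into hours, and it names only the Day 2 and Day 30 visits. The Day 29 entry has no mark, and the row is labelled in days.

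**Assignment of adverse events.** SAP 11.2.2 assigns each unsolicited AE to a dose, using Days 1 to 28 for Dose 1 and Days 29 to 57 for Dose 2 in the two-dose regimens. The footnotes to shells 14.3.1.2.2 and 14.3.1.2.6 define the Dose 1 period differently: the vaccination day plus 28 days, ended early by the second CV7202 dose. SAP 11.2.1 counts solicited AE days per diary, with one diary per dose.

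**Reporting.** SAP 11.3 lists vaccination data and tabulates time between visits. Shell 14.3.6 shows only the number of doses received.

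**The concern.** A site working from Table 2.1 may give Dose 2 before Day 29 and be in window. The same act is contrary to 5.2 and to the description in 5.7 and SAP 4. No passage says which takes precedence or bars Dose 2 before Day 29. It is therefore unclear whether a second dose at 26 or 27 days is a deviation, and SAP 9.2 leaves deviations to a data review meeting without a criterion for this case.

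Also at stake is which dose an unsolicited event is charged to. A split at fixed study days is sound only if every second dose falls on the nominal day, and the window allows four other days. In groups of 8, moving one event between doses is visible in a by-dose table.

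**Working it through.** **Inputs.** Dose 1 is on Day 1 (Visit 3). Dose 2 is at Visit 8, nominal Day 29. The window is plus or minus 2 days and the stated minimum is 28 days. Two-dose subjects: 8 in Group 3a and 8 in Group 4a, so 8 + 8 = 16 planned (Table 8.1).

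**Reading the table.** The day, window and visit-number rows of Table 2.1 each hold 23 entries. Matched one to one, the ninth entries are Day 29, plus or minus 2, and Visit 8. The neighbouring columns fit: Day 8 has +1, Day 30 has the hour-based entry, and Day 36 has -1/+2.

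**The plan's own figure.** Nominal interval = 29 − 1 = 28 days, which just meets the minimum.

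**With the window.** Earliest day 29 − 2 = 27; latest day 29 + 2 = 31. For Dose 2 on Day d, the interval is d − 1, and the vaccination day plus 28 days runs from d to d + 28. The Dose 1 period before any early cut-off ends on Day 1 + 28 = Day 29.

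| Dose 2 day | Interval (days) | At least 28? | Period after Dose 2 | Where the fixed split (1–28, 29–57) goes wrong |
|---|---|---|---|---|
| 27 | 26 | No | 27–55 | Days 27–28 go to Dose 1; Days 56–57 go to Dose 2 although past 28 days |
| 28 | 27 | No | 28–56 | Day 28 goes to Dose 1; Day 57 goes to Dose 2 although past 28 days |
| 29 | 28 | Yes | 29–57 | None |
| 30 | 29 | Yes | 30–58 | Day 29 goes to Dose 2 before it is given; Day 58 is missed |
| 31 | 30 | Yes | 31–59 | Days 29–30 go to Dose 2 before it is given; Days 58–59 are missed |

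Two of five permitted days are below 28, and the largest shortfall is 28 − 26 = 2 days. The fixed split matches the actual dosing periods on one day of the five. On the other four it also departs from the shell footnotes, which follow actual vaccination. After Dose 2 on Day 27, for example, an event on Day 28 belongs to Dose 1 under SAP 11.2.2 but is excluded from the Dose 1 tables by their footnotes.

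**The case against.** The best reply is that the passages can be applied together. Table 2.1 sets a window for a visit with many procedures, attended also by subjects who are not dosed that day, while 5.2 restricts the CV7202 pair; Days 29 to 31 satisfy both. That reading is possible, but the documents do not state it. The table can express a no-earlier-than limit, since the Day 8 vaccination visit has a plus-only window, and it does not do so for Day 29.

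Stronger readings are tempting and are not supported:
- **The window pushes Dose 2 into Dose 1 follow-up.** Unsolicited follow-up is Days 1–29, so a dose exactly on Day 29 already touches it. Early dosing lengthens the overlap but does not create it.
- **Dose 2 reactions will generally be counted under Dose 1.** Solicited reactions are tied to per-dose diaries, with a new one issued at Visit 8, and the Dose 1 shells stop at Dose 2. Only the fixed-day rule for unsolicited events is exposed.
- **Section 6.3 sends sites to the window to dose early.** It concerns doses delayed by infection, other acute disease or fever, so it covers late dosing only.
- **The dose justification fails.** Section 5.7 rests mainly on no-adverse-effect-level dose margins. The interval is a supporting contrast with weekly dosing, and 26 days is still 26/7 = 3.7 weeks.
- **Every interval under 28 days is a deviation.** That presumes the 28-day statement prevails, which the documents leave open. Protocol 10.2 excludes subjects not dosed on the scheduled date from the per-protocol sets, but SAP section 12 drops those sets.

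It can also be argued that the day numbers in SAP 11.2.2 are shorthand, since the sentence before them speaks of 28 days after vaccination. That may be the intent, but as written a programmer could follow either rule.

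**Conclusion.** The contradiction stands. Protocol 5.2, 5.7 and SAP 4 state a minimum of 28 days; Table 2.1 permits 26 or 27. It affects two of five permitted days and up to 16 planned two-dose subjects, by at most two days. No effect on a primary or secondary endpoint has been shown, and the documents do not say whether any subject was dosed early. A reader should not infer that any subject was, or that safety was compromised.

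The conflict between the fixed-day split in SAP 11.2.2 and the shell footnotes is also real. It arises whenever Dose 2 is given off Day 29, in either direction.

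This rests on the one-to-one column match in Table 2.1, on the Day 29 window being in days as labelled, and on the planned group sizes. It takes no position on which interval is right.

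**What to change.** 1. Reconcile the Visit 8 window in Table 2.1 with protocol 5.2, 5.7 and SAP 4, so that one statement governs the interval to CV7202 Dose 2. The sponsor decides which.
2. In SAP 11.2.2, replace the fixed day split with assignment by each subject's actual Dose 2 date, in line with the shell footnotes. The same rule can serve Rabipur Dose 3, which shares Visit 8.
3. Derive the Dose 1 to Dose 2 interval from recorded vaccination dates, tabulate it for the 2x1 µg and 2x2 µg regimens, and report any interval under 28 days. Deviation status then follows from the reconciled rule. SAP 11.3 already tabulates time between visits, so this isolates one interval and labels it.

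SAP 6.4 records 53 subjects vaccinated and observed to Day 57 by the second interim analysis, including 16 at each of the two lower doses. Changing a window now cannot alter any dose; the value lies in clear reporting. If no interval is under 28 days, one sentence in the report settles the interval question. The cost is one derived variable, a minor table and a short SAP edit, with no new data.
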